- For the first time, we will establish the preliminary efficacy of VVC-delivered, massed imaginal exposure for PTSD. While these findings will be preliminary as the study is not powered for efficacy, it will provide preliminary estimates of pre- to post- effect sizes and variance in outcomes that will aid in planning well-crafted and properly statistically powered follow up RCTs.
- COVID-19 has fundamentally altered the delivery landscape for clinical and research practice. The methods proposed here further advance the VA's capacity to promote evidence-based care and research amidst unforeseen disruptions to in-person procedures.
- For the first time, we will establish acceptability among stakeholder providers, of VVC-delivered, massed imaginal exposure for PTSD. While in-person, massed imaginal exposure has been effective in RCTs, the perceptions of evidence-based clinical providers at the forefront of treating veterans have not been assessed. In order to assess implementation likelihood, as well as to assess the need to disseminate findings and techniques, input from provider stakeholders is essential.

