#### 4.0 Inclusion and Exclusion Criteria/ Study Population

Veterans who are aged 18-65 (inclusive), who meet full DSM-5 criteria for current PTSD will be recruited from all racial, ethnic and gender categories. The rationale regarding a cutoff of 65 years was for correspondence to prior massed in-person protocols (e.g., Zoellner et al, 2017). Planned follow up studies will include a broader age range and will be powered to analyze age effects on outcomes. To contend with dropout, we propose to enroll 25 veterans, with the aim of completing assessments and treatment for 20 participants. In-person investigations have shown a dropout rate of 5% (Sciarrino et al. 2020), thus a 20% allowance will ensure adequate recruitment to meet study aims.

**Exclusion Criteria.** Participants will be excluded for the following: 1. clinically unstable physical illness; 2. bipolar Type I disorder; 3. dementia; 4. repeated abuse or dependence upon drugs within 3 months; 5. unstable psychotropic regimen within 6-weeks; and finally, 6. active suicidal ideation or a suicide attempt within the past year.

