## 9.0 Study Design / Methods

### Overview.

This pilot project will implement an open-label single-arm design to address our specific aims to establish the safety, feasibility, tolerability and acceptability of massed imaginal exposure therapy for PTSD delivered via telehealth to Veterans with PTSD, and to obtain a preliminary estimate of efficacy (i.e., to support adequately powered follow-up studies employing group-randomized designs). All participants (***N = 25***) will receive a total of six-60 min. therapy sessions, delivered via VVC or a comparable VA-approved platform. Outcome assessments consisting of clinician-administered interview measures, self-report measures, and collection of remote affective and physiological indices derived from webcam footage will occur at pre-treatment, and at 1-week and 1-month following

treatment completion. Assessment instruments and procedures are detailed in the following sections.

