### Primary Outcome Measures

**Treatment Dropout/Completion.** We will collect data on treatment completion, to include the number of treatment sessions and assessment visits attended, via chart review from CPRS.

**Treatment Non-Compliance.** We will collect data on treatment compliance, including completion of in-session and between-session assignments, as determined by chart review and self-report.

**Satisfaction with Therapy and Therapist Scale - Revised (STTS-R).** The STTS-R is a 13-item Likert-type self-report scale designed to assess patient satisfaction with therapeutic services and providers (Oei & Green, 2008). This instrument will be administered at the post-treatment and 1-month follow-up time-points.

**Technology and Treatment Satisfaction Questionnaire (TTSQ).** The TTSQ is a 14-item self-report measure developed by the investigators. Items assess satisfaction, acceptance, tolerability, perceived utility and treatment outcome-related expectancies related to incorporating the remote affective physiology procedures into the assessment procedures (see below), as well as opinions about incorporating such measures into routine care. Both patients and

providers will complete slightly different versions of this measure, addressing the same items, but adapted appropriately for wording. This instrument will be administered at the post-treatment time-point.

**Clinician-Administered PTSD Scale for DSM-5 (CAPS-5).** The CAPS-5 is a structured interview for diagnosis of PTSD and is widely considered the gold-standard assessment (Blake et al., 1995; F. W. Weathers et al., 2018). The CAPS-5 will be administered at pre-treatment, post-treatment, and the 1-month follow-up visits, and will be used to evaluate inclusion criteria and as a comparative criterion to assess relations between our objective measurements and severity of trauma-related symptoms and functional impairments.

**PTSD Symptom Checklist for DSM-5 (PCL-5).** The PCL-5 is a 20-item self-report measure of PTSD symptom severity based on the DSM-5 (Wortmann et al., 2016). This measure will be administered at pre-treatment, post-treatment, and the 1-month follow-up, serving as a primary self-report outcome measure. It will also be administered at the beginning of each treatment session, to index trajectories of change over the course of treatment.

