**Patient Health Questionnaire (PHQ-9).** The PHQ-9 is a 9-item widely used self-report instrument that assesses core symptoms of major depression (Kroenke, Spitzer, & Williams, 2001). As with the PCL-5, the PHQ-9 will serve as a primary outcome measure administered at pre-treatment, post-treatment, and the 1-month follow-up, and just prior to each treatment session.

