## 10.0 Data Management

**Data Acquisition.** If (and only if) ultimately approved by the VA, we propose the use of VA Qualtrics, which is a secure, FedRAMP-authorized online data capture system that is widely used as a HIPPA-compliant web-based means to collect sensitive research data. Moreover, if approved, in addition to remotely collecting validated self-report questionnaire data from participants using this platform, we also request leveraging Qualtrics' functionality to integrate java script, which would enable us to directly capture audio and visual data from the participant's side from their webcam and microphone. This is an excellent alternative to our initially proposed procedures, which involve collecting streamed, then captured (i.e., on the clinician's side) footage. This is problematic due to significant temporal distortion and low sampling rate for screen-captured footage on currently deployed telehealth platforms approved by the VA (i.e., Teams, Webex, and VVC). As mentioned, the use of Qualtrics will be entirely contingent on obtaining full MUSC IRB and VA R&D approval for our proposed use. If ultimately not approved, we will continue to implement our procedures that involve capturing questionnaire data with hard copies, by mail.

**Data Preparation.** Pre-processing of data as the study progresses will allow for more expedient dissemination of study findings. As appropriate, pre-processing will follow standard best practices to ensure excellent data quality and security. Prior to analyses, data will be visually and statistically inspected for the presence of aberrant data points, which will be omitted prior to analyses.

**Analytical Plan.** Descriptive statistics will be reported for safety, feasibility, tolerability, and acceptability. Linear mixed-effects models will be used to characterize trajectories of change in symptoms and impairment, while controlling for potential confounders, such as baseline severity.

Following standard pre-processing steps, analyses will be conducted using generalized linear models, and will proceed in a bottom-up manner involving selection of the best fitting fixed and random growth terms, followed by adding predictors of interest. Factors (e.g., sex) will be dichotomously coded, whereas all continuous predictors will be scaled and centered as a function of baseline values to allow for meaningful interpretation of effects as indicative of reliable change.

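### The rule for omitting outlying data is not limited to errors, so valid extreme symptom scores could be removed from the exploratory effect-size and variance estimates

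*Combined protocol and SAP*

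**What the plan says.** Section 10.0, Data Preparation, states that "data will be visually and statistically inspected for the presence of aberrant data points, which will be omitted prior to analyses". The only qualifier is the sentence before it: "As appropriate, pre-processing will follow standard best practices to ensure excellent data quality and security". That sentence gives no cut-off, no check against source, and no distinction between a faulty value and a genuine extreme one. Nothing elsewhere in the document supplies these.

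The Analytical Plan follows directly: "Linear mixed-effects models will be used to characterize trajectories of change in symptoms and impairment". Under Primary Outcome Measures in section 9.0 the CAPS-5 is listed, the PCL-5 is described as "serving as a primary self-report outcome measure", and "the PHQ-9 will serve as a primary outcome measure".

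On purpose, section 2.0 says of the efficacy findings that "it will provide preliminary estimates of pre- to post- effect sizes and variance in outcomes that will aid in planning" later trials. The section 9.0 Overview gives the same reason: "to support adequately powered follow-up studies employing group-randomized designs". Section 4.0 plans to enrol 25 Veterans "with the aim of completing assessments and treatment for 20 participants".

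**The concern.** Omission is stated as what will happen to any point judged aberrant, and the rule applies to data in general. A valid symptom score far from the others can meet that description. A Veteran who gets worse while most improve is a natural candidate, and removing that score favours the treatment.

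Two quantities are at stake. Dropping valid tail values shrinks the SD, which is one of the outputs promised for planning. It also tends to raise the standardized change, and if the dropped scores belong mostly to people who worsen, the mean change is biased as well. The study is open-label with one arm, pre-processing runs while the study is in progress, and the plan does not say that the person judging a value is kept from the results. A later reader could neither see nor undo the deletions.

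**Working it through.** **Sample size.** Twenty completers with a 20% allowance give 20 / (1 − 0.20) = 25, which matches section 4.0. So n = 20 is used below. The plan gives no SD, numerical effect size, alpha or power, so there is no efficacy figure to reproduce.

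**Assumptions (not from the documents).** Normal data; equal SDs at both visits; true improvement of 0.8 SD of change; correlation rho between visits of 0.3, 0.5 or 0.7. A raw score is deleted if |x − visit mean| > c × visit SD, using sample values in one pass. Here d = mean change / SD of change, from complete pre-post pairs. Every flagged score is deleted without judgement, so the results are nearer an upper bound for each c.

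**Symmetric data, no errors present** (simulated; values for rho 0.3, 0.5, 0.7; SDs and d as ratios to no deletion):

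| c | P(at least one valid score dropped) | SD of change | Post-treatment SD | Mean d |
|---|---|---|---|---|
| 2 | 0.858, 0.856, 0.842 | 0.930, 0.949, 0.968 | 0.898 | 1.084, 1.060, 1.037 |
| 2.5 | 0.236, 0.234, 0.224 | 0.983, 0.988, 0.993 | 0.973 | 1.020, 1.014, 1.009 |
| 3 | 0.020, 0.020, 0.018 | close to 1 | 0.997 | 1.002, 1.002, 1.001 |

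At 2 SD the SD of change falls 3% to 7% and mean d rises about 4% to 8%. Mean change does not move. The rise in d is an average: at 2 SD, d falls in 35% to 43% of simulated trials.

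**One of 20 worsens by 1.5 SD of change.** With all data kept:
- expected mean improvement = (19 × 0.8 − 1.5) / 20 = 13.7 / 20 = 0.685 SD of change;
- expected variance = 1 + (0.8 + 1.5)² / 20 = 1 + 5.29 / 20 = 1.26, so the SD is about 1.12;
- d ≈ 0.685 / 1.12 = 0.61, in line with the simulated median of about 0.62.

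If the worsening Veteran were always removed, mean improvement would return to 0.8, a rise of 0.8 / 0.685 − 1 = 17%. That Veteran is flagged in only some samples, so the average bias is smaller:

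| c | Mean change biased upward by | Median d (from about 0.62) |
|---|---|---|
| 2 | about 5% to 11% | 0.70 to 0.80 |
| 2.5 | about 3% to 8% | 0.65 to 0.71 |
| 3 | up to about 3% | 0.62 to 0.64 |

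**Effect on planning (symmetric case).** For a fixed difference, sample size scales with SD². At 2 SD the SD of change gives 0.930² = 0.865 to 0.968² = 0.937, so a later trial would be about 6% to 14% too small. At 2.5 SD, 0.983² = 0.966 to 0.993² = 0.986, about 1% to 3% too small. The SD is only one input to a group-randomized design.

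**Against sampling error.** With 19 degrees of freedom, the 95% chi-square limits for an SD are 0.760 to 1.461 times the estimate (−24% to +46%). The sampling SD of d is about 0.28; the average shift in the symmetric case is at most 0.07.

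**The case against.** The strongest reply is that the sentence is ordinary data cleaning aimed at webcam signals. Section 10.0 itself reports distortion in captured footage, and best practice would not call a valid in-range questionnaire score aberrant. The authors may well have had this in mind. The text does not say so, however. The paragraph before the rule covers questionnaire data as well as audio and video, and the models named after it are for symptoms and impairment. Artefact correction for video heart rate already has its own steps in section 9.0, and the facial measures are said to follow a similar approach.

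A second reply is that the size rests on an assumed automatic cut-off, whereas the plan includes visual inspection. That stands: the 2 SD figures come from the harshest cut-off shown, and at 3 SD with symmetric data nothing of note happens.

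A third is that the PCL-5 and PHQ-9 are also collected at every session and analysed with growth models, which the two-visit calculation does not mimic. A small nine-occasion growth-model check (250 replicates, assumed variances, some convergence warnings) gave d up about 5% at 2 SD, 1% at 2.5 SD and none at 3 SD. The mismatch does not change the picture.

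A reader might infer that the plan intends to delete valid scores or to hide worsening. The documents do not support that: deletion of valid scores is permitted, not stated as a plan. Nor do they support a threat to the safety results. Adverse events and suicidality are monitored separately (section 11.0), and safety, feasibility, tolerability and acceptability are reported descriptively.

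**Conclusion.** The point holds as a minor one. The omission rule is not confined to errors or artefacts, so it leaves room to drop valid CAPS-5, PCL-5 or PHQ-9 scores and thereby bias the exploratory effect-size and variance estimates. How far depends on a cut-off the plan does not give. Under the stated assumptions it ranges from negligible (3 SD, symmetric data) to a few per cent in d (2 SD, symmetric data). It is clearly larger at 2 or 2.5 SD if even one of 20 Veterans truly worsens, because the mean change then moves too.

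It would go too far to say that the pilot's efficacy estimates are unusable or that d is always inflated. Efficacy is Exploratory Aim 2 and is described as unpowered. With symmetric data the average shift is well inside sampling error, and d falls in a sizeable share of trials. Unlike sampling error, though, the shrinkage of the SD is systematic and no confidence interval would reveal it.

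**What to change.** Replace the sentence in Data Preparation with:

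> Values are removed only if source checking shows a recording or entry error, or if the video/audio pipeline flags a signal artefact by pre-set rules applied without reference to outcome; all valid clinician-rated and self-report scores are kept in the main analysis.

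Add that any analysis setting valid scores aside is a sensitivity analysis only, reported beside the main result. A short log of removals with reasons would be good practice.

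The cost is one sentence, a slightly larger SD and a little more analysis work. Legitimate cleaning of entry errors and signal artefacts is unaffected. If faulty data were all the authors meant, this simply puts their intent on paper.

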## 1.0 Objectives / Specific Aims

The goal of this project is to establish the safety, feasibility, and acceptability of abbreviating and accelerating telehealth-delivered imaginal exposure therapy for post-traumatic stress disorder (PTSD). Importantly, conventional telehealth-delivered Prolonged Exposure (PE) therapy is non-inferior to the conventional, gold standard in-person PE for PTSD (Acierno et al., 2017). Intensive or massed schedules of in-person exposure- based trauma-focused treatments have likewise recently been shown, in a nascent but promising literature, to produce comparable treatment outcomes to conventional once or twice weekly schedules, but importantly, with lower levels of premature dropout (Sciarrino et al., 2020; Zoellner et al., 2017).

**AIM 1: Establish the safety of VVC-delivered massed imaginal exposure for PTSD.** We hypothesize that VVC-delivered, massed imaginal exposure will be safe as indexed by no significant adverse events.

**AIM 2: Establish the feasibility, tolerability, and acceptability of VVC-delivered massed imaginal exposure for PTSD.** We hypothesize that 1) veterans will consider the treatment acceptable and tolerable and that 2) recruitment and retention will be feasible (> 80% retention).

**EXPLORATORY AIM 1: Establish acceptability among stakeholder providers of VVC-delivered massed imaginal exposure for PTSD.** We hypothesize that 1) telemental healthcare providers will consider the treatment acceptable and tolerable and that 2) will be willing to receive training and/or refer patients to such services.

**EXPLORATORY AIM 2: Establish the preliminary efficacy of VVC-delivered massed imaginal exposure for PTSD.** We hypothesize that 1) veterans will demonstrate moderate reductions in posttraumatic stress and associated symptoms and impairment from intake to the end of treatment that will in turn, 2) be maintained or extended at the 1-month post-treatment follow-up.

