## **Secondary Outcome Measures**

**Posttraumatic Cognitions Inventory, 9-Item Version (PTCI-9).** The PTCI-9 is a 9-item well-validated self-report measure of maladaptive beliefs that commonly manifest in PTSD (Wells et al., 2019). This measure will be administered at pre-treatment, post-treatment, and the 1-month follow-up, and at the beginning of each session to index change in problematic trauma-related beliefs.

**Mood and Anxiety Symptom Questionnaire (MASQ).** The MASQ is a brief 26-item questionnaire with three separate subscales including general distress, anxious arousal, and anhedonic depression (Casillas & Clark, 2000). This measure will be administered at pre-treatment, post-treatment, and the 1-month follow-up.

**PTSD Safety Behaviors Questionnaire (PSBQ).** The PSBQ is a 10-item validated measure of unnecessary protective actions, including avoidant behaviors, that are common in cases of PTSD, and are widely believed to serve to maintain and exacerbate trauma-related symptoms (Foulser & Telch, 2019). This measure will be administered at pre-treatment, post-treatment, and the 1-month follow-up.

**Emotional Reactivity and Numbing Scale (ERNS).** The ERNS is a 62-item self-report measure that assesses tendencies to experience a restricted range of emotions, or emotional numbing, including in response to emotionally arousing situations (Orsillo, Theodore-Oklota, Luterek, & Plumb, 2007). This instrument will be administered at the pre-treatment assessment visit.

**Sheehan Disability Scale (SDS).** The SDS is a 5-item measure that assesses disability and functional impact associated with symptoms (Leon, Shear, Portera,

& Klerman, 1992). This instrument will be administered at the pre-treatment, post-treatment and 1-month follow-up assessment visits.

**Clinical Global Impressions (CGI).** The CGI is a 5-item, clinician-rated measure that provides a global assessment of severity, functioning, and improvement over the course of treatment (Kadouri, Corruble, & Falissard, 2007). This measure will be administered at the pre-treatment, post-treatment, and 1-month follow-up assessment time-points.

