Additionally, all models will control for baseline levels of the outcome to control for individual differences at pre-treatment in estimating effects. Model refinement will be guided by theory, evaluating standard fit statistics (e.g. Log Likelihood, AIC, BIC, etc.) and whether modeling assumptions are sufficiently met.

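### Three-visit outcomes (CAPS-5, SDS, MASQ, PSBQ): fit-selected growth models with baseline adjustment can make pre-to-post intervals too narrow; prespecified visit contrasts avoid this

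*Combined protocol and SAP*

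**What the plan says.** Exploratory Aim 2 (section 1.0) states two hypotheses: that "veterans will demonstrate moderate reductions in posttraumatic stress and associated symptoms and impairment from intake to the end of treatment", and that the gains will then "be maintained or extended at the 1-month post-treatment follow-up".

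The outcomes at issue have three measurements each. In section 9.0, "The CAPS-5 will be administered at pre-treatment, post-treatment, and the 1-month follow-up visits"; for the SDS, "This instrument will be administered at the pre-treatment, post-treatment and 1-month follow-up assessment visits"; MASQ and PSBQ follow the same schedule. PCL-5, PHQ-9 and PTCI-9 differ, because they are also completed before every session.

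Section 10.0, Analytical Plan, says: "Linear mixed-effects models will be used to characterize trajectories of change in symptoms and impairment, while controlling for potential confounders, such as baseline severity". It then says that the analysis "will proceed in a bottom-up manner involving selection of the best fitting fixed and random growth terms", with predictors added afterwards. It adds that "all models will control for baseline levels of the outcome to control for individual differences at pre-treatment in estimating effects", and that "Model refinement will be guided by theory, evaluating standard fit statistics (e.g. Log Likelihood, AIC, BIC, etc.) and whether modeling assumptions are sufficiently met".

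The plan lists no candidate shapes and no selection rule, does not name the contrast that estimates pre-to-post change, and does not say whether the pre-treatment score is a response row as well as a covariate. Section 2.0 (Impact and innovation) says that the pilot's pre-to-post effect sizes and outcome variances should help to plan later trials.

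**The concern.** With three visits, the two changes that Exploratory Aim 2 asks about, pre to post and post to 1 month, are the whole trajectory. There is no further shape to discover. Choosing a shape by fit in 20 to 25 Veterans can only keep those two changes or replace them with something simpler, and the reported interval ignores that a choice was made.

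The baseline adjustment raises a second question. If the pre-treatment score is both an outcome row and a predictor of that same row, the model's picture of how people vary around the mean change may be wrong.

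At stake are the standard error and the SD of pre-to-post change, which matter for the planning use in section 2.0, and the reading of whether gains were held or extended.

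**Working it through.** **Inputs from the documents.** Section 4.0: 25 enrolled for 20 completers with a 20% allowance; 20 / (1 - 0.20) = 25, which reproduces. Three visits for the four outcomes (section 9.0). Latest visit days from the stated windows: start within 1 week, 10 days of treatment, 1 week to post-treatment, so 7 + 10 + 7 = day 24; 1 month after treatment is 7 + 10 + 30 = day 47.

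**Assumed, because the documents give no figures.** SD 1 at each visit; correlations pre-post / pre-1-month / post-1-month of 0.5/0.5/0.8, 0.6/0.6/0.7 or 0.5/0.5/0.5; a true drop of 0.5 or 0.8 SD (the word moderate has no number), or 1.15 to 2.93 SD (the range cited in section 2.0), then flat. The true SD of change is sqrt(2(1 - r)): 1.00 for r = 0.5 and 0.89 for r = 0.6. Most runs had 20 completers, alone or with 5 more lost at random after baseline. Candidates: linear or quadratic mean (a quadratic through three visits equals visit means), with random intercept or random intercept plus slope. Selection is by ML, then a REML refit. Each setting used 250 to 1,000 simulated data sets, so a single percentage has a standard error of roughly 1 to 3 points.

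**Reading A: the pre-treatment score is a response row and a covariate.**

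*Shape chosen by fit.* Take true means 0, -0.5, -0.5 at days 0, 24, 47. The mean day is 71/3 = 23.67 and the mean outcome is -0.333. The sum of cross-products is -11.83 and the sum of squared day deviations is 560.1 + 0.1 + 544.4, about 1104.67, so the least-squares slope is -11.83 / 1104.67 = -0.01071 per day. The line gives -0.01071 x 24 = -0.26 pre to post, about half the true drop, and -0.01071 x 23 = -0.25 afterwards, where the truth is 0. Fit often prefers that line at this effect size:

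| True drop, then flat | AIC coverage | BIC coverage |
|---|---|---|
| 0.5 SD, line or quadratic | 73-79% | 64-69% |
| 0.5 SD, drop-then-plateau also a candidate | 81-86% | 81-86% |
| 0.8 SD, line or quadratic | 85% | 78-80% |
| 1.15 SD, line or quadratic | 86-89% | 86-89% |

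At 1.15 SD a line is chosen in at most 3% of data sets, and at 2.0 SD and above never, so the shortfall left there is not due to shape. Averaged over data sets, the estimate at 0.5 SD falls short by only 0.01-0.06 SD under AIC or BIC. The fault is mainly in the interval.

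*Baseline as response and covariate, shape fixed at visit means.* Baseline is constant within a person, so with a random intercept it cancels from the within-person contrast: standard error 0.2207 without it and 0.2195 with it, coverage 95.3% and 95.2% (20 complete cases, equal correlations of 0.5). With a random slope it does matter. The covariate soaks up most of the spread in the pre-treatment row, so the remaining spread fans out over time. A random slope fits that fan, but it forces the spread of change to keep growing from day 24 to day 47, and so understates it at day 24. AIC chose a random slope in about 76% to 99.6% of such fits. With random terms selected, coverage was about 85-90% under the first two correlation sets and about 90-94% under equal correlations of 0.5. The model-implied SD of change was about 0.72-0.90 where the truth is 0.89-1.00.

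**Reading B: the pre-treatment score is a covariate only.** Two response rows remain, so the growth terms describe post-treatment to 1 month. The pre-to-post change has to be recovered as the intercept minus the baseline mean. Using the model's standard error, that covers 91-95%.

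**Comparator.** Paired or unstructured visit contrasts without the covariate covered about 93-97% across all runs.

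**The case against.** The plan never states reading A. It is tempting to infer it because two response rows leave no curvature to select, but the same paragraph also serves the session-level PCL-5, PHQ-9 and PTCI-9, where growth selection makes sense. That stands: the text is ambiguous, although its reference to impairment does reach the SDS. Under reading B the intervals are close to nominal, and the complaint is only that the wanted change is not a term in the model.

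The low coverage figures depend on a candidate list that the plan does not give. Refinement is to be guided by theory, and the wording of Exploratory Aim 2 supports a drop-then-plateau candidate. That stands too, and is why 81-86% is given beside the lower figures. It does not restore 95%.

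A reader might infer that adjusting for baseline narrows the interval by itself. It does not: with a random intercept the effect is negligible. Under AIC at a 0.5 SD drop (equal correlations), the covariate even raised coverage, from 68% to 75%, because a line was chosen less often.

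A reader might also infer that a later trial would be badly undersized, since (0.72/1.00)^2 = 0.52. The documents do not support that step. Section 2.0 promises effect sizes and variance in outcomes, not a model-implied SD of change; the observed SD is available whatever model is fitted; and no method for sizing the later trials is given.

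**Conclusion.** The point holds conditionally and is modest. If the pre-treatment score is a response row, fit-selected shape brings coverage for a maintained 0.5 SD drop down to about 64-79% with a line and quadratic as candidates, or 81-86% with a plateau candidate added. Selecting a random slope with baseline on both sides of the model gives about 85-94% at any effect size. If the score is only a covariate, the model does not directly estimate what Exploratory Aim 2 asks.

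These figures rest on the assumed SDs, correlations, visit days and effect sizes, and on dropout at random or none. Other theory-based choices, checks of residual spread by visit, and informative dropout were not simulated. The plan promises no interval or test for this aim, describes the study as not powered for efficacy, and leaves safety and feasibility to descriptive statistics, so nothing here touches the two main aims.

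**What to change.** For CAPS-5, SDS, MASQ and PSBQ, prespecify visit as a three-level category with unstructured covariance, fitted by REML with Kenward-Roger degrees of freedom, with the pre-treatment score as a response and not as a covariate. Report post minus pre and 1-month minus post, each with a 95% interval, and the observed SD of change. With complete data these are paired t contrasts.

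Partial changes help less. Dropping the covariate but still selecting the shape gives 64-69% (AIC) or 44-58% (BIC) at 0.5 SD. Visit categories without the covariate but with a random-effects covariance give 91-96%, so the unstructured covariance adds only a little more.

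Keep fit-selected growth models as secondary descriptions of the session-level PCL-5, PHQ-9 and PTCI-9, list their candidate shapes, and state whether the pre-treatment score is a response row.

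The cost is plan wording and no new data. Intervals for pre-to-post change become wider: half-width about 0.40-0.45 SD, against 0.26-0.33 SD under the plan's approach. The contrasts do not address the lack of a control arm or informative dropout.
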